1. BACKGROUND

This Statistical Analysis Plan (SAP) provides details of the planned analyses and statistical methods for Study WO29636 (IMvigor010). The analyses described in this SAP will supersede those specified in Protocol WO29636.

2. STUDY DESIGN

Study WO29636 is a global Phase III, open-label, randomized, controlled trial designed to evaluate the efficacy and safety of adjuvant treatment with atezolizumab compared with observation in patients with muscle invasive urothelial carcinoma (UC), who are at high risk for recurrence following resection. The study schema is provided in [Figure 1](#).

Figure 1 Study Schema

IC = tumor-infiltrating immune cell; IV = intravenous; n = number; PD-L1 = programmed death-ligand 1; q3w = every 3 weeks; UC = Urothelial carcinoma.

Patients were randomized to one of the following arms in a 1:1 ratio:

- Arm A (experimental arm): atezolizumab 1200 mg q3w
- Arm B (control arm): observation

The randomization was stratified by the following factors: number of lymph nodes resected (< 10 vs. ≥ 10), nodal status (positive vs. negative), tumor stage after surgical resection (\leq pT2 vs. pT3/pT4), PD-L1 status (IC0/1 vs. IC2/3), and prior neo–adjuvant chemotherapy (yes vs. no).

Note: The study design was revised in Protocol Version (v) 6 from a diagnostically selected population with PD–L1 status (tumor–infiltrating immune cell [IC] score measured in tumor) of IC2/3 to include all patients regardless of PD–L1 status. Age–adjusted Charlson comorbidity index, which was a stratification factor prior to Protocol v6, was removed as a stratification factor in Protocol v6 and replaced with PD–L1 status (IC0/1 vs IC2/3). Patients enrolled prior to Protocol v6 have been categorized as IC2/3 for stratification purposes.

For patients in Arm A, atezolizumab will be administered intravenously (IV) on Day 1 of each 21-day cycle for 16 cycles (up to 1 year). In Arm B, patients will continually undergo observation starting on Day 1 of each 21-day cycle for 16 cycles (up to 1 year).

Treatment/observation will be discontinued in the event of disease recurrence, unacceptable toxicity, withdrawal of consent, or study termination by the Sponsor. Patients in the control arm will not be allowed to cross over to receive atezolizumab treatment within this study.

All patients will undergo scheduled assessments for tumor recurrence at baseline and every 12 weeks (approximately every 4 cycles) in the first year following randomization. Upon completion of the treatment/observation period, surveillance for tumor recurrence will be performed every 12 weeks for years 2-3; every 24 weeks for years 4-5; and at year 6 (approximately 48 weeks after the last assessment in year 5). In the absence of a disease-free survival (DFS) event (defined as any of the following: local [pelvic] recurrence of UC; upper urinary tract or urethral recurrence of UC; distant metastasis of UC; or death from any cause), surveillance for tumor recurrence should continue regardless of whether patients start new anticancer therapy, until withdrawal of consent, loss to follow-up, or study termination by the Sponsor, whichever occurs first.

The primary efficacy endpoint is DFS as assessed by the investigator and the key secondary endpoint is overall survival (OS). See Section 2.2 for further details on primary efficacy endpoints, as well as secondary and other safety, pharmacokinetic (PK), and exploratory endpoints.

There are no interim analyses planned for DFS and two interim analyses are planned for OS in this study. See Section 2.3 for detailed analysis timing.

An external independent Data Monitoring Committee (iDMC) was convened to evaluate safety data on an ongoing basis.

2.1 PROTOCOL SYNOPSIS

The Protocol Synopsis is in [Appendix 1](#). For additional details on study assessments, see the Schedule of Assessments in [Appendix 2](#).

2.2 DETERMINATION OF SAMPLE SIZE

Approximately 800 patients will be randomized in this study.

2.2.1 Type I Error Control

The Type I error (alpha) for this study is 0.05 (two-sided). Type I error will be controlled for the primary endpoint of DFS and the key secondary endpoint of overall survival (OS).

To control the Type I error at $\alpha=0.05$ (two-sided) for DFS and OS endpoints, the treatment arms will be compared in a hierarchical fashion as follows:

- If the DFS analysis results are statistically significant at $\alpha=0.05$ (two-sided), then the analysis of OS will be performed at $\alpha=0.05$ (two-sided) and the interim analysis boundaries for OS (see Section 2.3.2) will be calculated according to $\alpha=0.05$ (two-sided).

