6.1.1 Type I Error Control

The type I error (α) for this study is 0.05 (two-sided). Type I error will be controlled for the primary endpoint of DFS and the key secondary endpoint of OS. To control the Type I error at $\alpha=0.05$ (two-sided) for DFS and OS endpoints, the treatment arms will be compared in a hierarchical fashion as follows: If the DFS analysis results (as defined for United States registrational purposes; see Section 6.4.1) are statistically significant at $\alpha=0.05$ (two-sided), then the analysis of OS will be performed at $\alpha=0.05$ (two-sided) and the interim analysis boundaries for OS (see Section 6.9.2) will be calculated according to $\alpha=0.05$ (two-sided).

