6.4.1 Primary Efficacy Endpoint

The primary efficacy endpoint is investigator-assessed DFS, defined as the time from randomization to the time of first occurrence of a DFS event, defined as any of the following: local (pelvic) recurrence of UC; urinary tract recurrence of UC; distant metastasis of UC; or death from any cause. Data for patients without a DFS event will be censored at the last date the patient was assessed to be alive and recurrence free as determined with radiographic evidence. Data for patients with no post-baseline disease assessment will be censored at the randomization date.

For United States registrational purposes, the primary efficacy endpoint of DFS will be defined as described above with an additional censoring rule for missed visits. Data for patients with a DFS event who missed two or more scheduled assessments immediately prior to the DFS event will be censored at the last tumor assessment as determined with radiographic evidence prior to the missed visits. Type I error control (see Section 6.1.1) will be applied to this analysis of DFS.

DFS will be analyzed in the ITT population. The following analyses will be performed for both DFS endpoints described above. DFS will be compared between treatment arms using the stratified log-rank test. The hazard ratio (HR) for recurrence or death will be estimated using a stratified Cox proportional hazards model and the 95% CI for the HR will be provided. The stratification factors will be the same as the randomization stratification factors (see Section 4.2); however, stratification factors may be combined for analysis purposes if necessary to minimize small stratum cell sizes. Combination of stratification factors, if any, would be specified in the Statistical Analysis Plan (SAP) prior to analysis. The stratification factors will be obtained from the IxRS at the time of randomization. Results from an unstratified analysis will also be provided. Kaplan-Meier methodology will be used to estimate median DFS for each treatment arm; Kaplan-Meier curves will be produced. Brookmeyer-Crowley methodology will be used to construct the 95% CI for the median DFS for each treatment arm. The DFS rate at various timepoints (i.e., every 6 months after randomization) will be estimated by Kaplan-Meier methodology for each treatment arm, and the 95% CI will be calculated using Greenwood's formula.

The following additional analyses will be performed for both DFS endpoints described above:

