4.4.1 Primary Efficacy Endpoint

The primary efficacy endpoint is Investigator-assessed DFS, defined as the time from randomization to the first occurrence of a DFS event, defined as any of the following:

- Local (pelvic) recurrence of UC
- Urinary tract recurrence of UC
- Distant metastasis of UC
- Death from any cause

Data for patients without a DFS event will be censored at the last date the patient was assessed to be alive and recurrence free as determined with radiographic evidence. Data for patients with no post-baseline disease assessment will be censored at the randomization date.

For U.S. registrational purposes, the primary efficacy endpoint of DFS will be defined as described above with an additional censoring rule for missed visits. Data for patients with a DFS event who missed two or more consecutive scheduled assessments immediately prior to the DFS event will be censored at the last date the patient was assessed to be alive and recurrence free as determined with radiographic evidence prior to the missed visits or at the randomization date if there is no post-baseline tumor assessment prior to the DFS event.

DFS will be analyzed in the ITT population. The following analyses will be performed for both DFS endpoints described above. Treatment comparisons will be based on the stratified log-rank test at the two-sided level of significance as described in Section 2.2.1. The stratification factors used for the analysis are described in Section 4.4 and the values will be those recorded in the IxRS. The null and alternative hypotheses can be phrased in terms of the survival functions $S_A(t)$ and $S_B(t)$ in Arm A (atezolizumab) and Arm B (observation), respectively:

$$H_0: S_A(t) = S_B(t) \text{ versus } H_1: S_A(t) \neq S_B(t)$$

The HR, λ_A/λ_B , where λ_A and λ_B represent the hazard of experiencing an DFS event in Arm A and Arm B, respectively, will be estimated using a stratified Cox regression model with the same stratification variables used for the stratified log-rank test, and the 95% CI for the HR will be provided. Results from an unstratified analysis will also be provided.

Kaplan-Meier methodology will be used to estimate median DFS for each treatment arm and to construct DFS curves for each treatment arm. The Brookmeyer-Crowley methodology will be used to construct the 95% CI for the median DFS for each treatment arm (Brookmeyer and Crowley 1982).

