4.4.2 Secondary Efficacy Endpoints

4.4.2.1 Overall Survival (OS)

Overall survival is defined as the time from randomization to the date of death from any cause, regardless of whether the death occurs during study treatment or following treatment discontinuation. Data for patients who have not died will be censored at the last date they were known to be alive. Data for patients without post-baseline survival information will be censored at the randomization date. Methods for comparison of OS between treatment arms will be the same as the methods for treatment comparison for the primary efficacy endpoint of DFS.

Three analyses of OS are planned (two interim analyses and one final analysis; see Section 2.3.2 for details). The first interim analysis of OS will occur at the time that the primary endpoint of DFS is analyzed. The Type I error control for the secondary endpoint of OS is described in Section 2.2.1.

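### Does the SAP leave open which of the two DFS analyses carries the type I error and opens the OS test?

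*SAP*

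**What the plan says.** Protocol 6.4.1 defines investigator-assessed DFS. It then defines a US registrational version, in which an event that follows two or more missed assessments is censored at the last assessment before the gap. Directly after that rule it says "Type I error control (see Section 6.1.1) will be applied to this analysis of DFS". Protocol 6.1.1 makes OS conditional on the same version: "If the DFS analysis results (as defined for United States registrational purposes; see Section 6.4.1) are statistically significant at" two-sided 0.05, OS is then tested at 0.05.

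SAP 2.2.1 gives the same hierarchy without the parenthesis: "If the DFS analysis results are statistically significant at" 0.05. SAP 4.4.1 defines both versions and says "The following analyses will be performed for both DFS endpoints described above" and "Treatment comparisons will be based on the stratified log-rank test at the two-sided level of significance as described in Section 2.2.1". It does not carry over the sentence that assigns type I error control. For OS, SAP 4.4.2.1 adds only "The Type I error control for the secondary endpoint of OS is described in Section 2.2.1".

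SAP section 1 says "The analyses described in this SAP will supersede those specified in Protocol WO29636". SAP 2.1 incorporates the synopsis by reference ("The Protocol Synopsis is in" Appendix 1). That appendix, labelled protocol version 8, contains both the type I error assignment and the condition for OS.

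**The concern.** With two versions of the primary endpoint and one alpha, a plan must say which version is confirmatory. The protocol does. The SAP's statistical sections do not, and the SAP claims precedence over the protocol. SAP 4.4.1 calls both versions the primary efficacy endpoint and refers both to the same significance level.

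The difficult case is a split result. If DFS were significant without the missed-visit rule but not with it, the protocol would stop there and OS could not be tested. SAP 2.2.1 and 4.4.1, read alone, do not say so. The first OS interim takes place at the DFS analysis, when the Sponsor's blinding ends, so any doubt would be settled with results in hand. On the most permissive reading, either DFS result could be claimed, and the false-positive rate would exceed 0.05.

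**Working it through.** **The plan's own figures.** Inputs from SAP 2.2.2: medians 20 and 26.7 months, two-sided alpha 0.05, 80% power, 1:1 allocation.

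- Events: 4 × (1.960 + 0.842)² / [ln(20/26.7)]² gives 377 after rounding up, as stated.
- Power at 377 events: 80.1%.
- Largest significant hazard ratio: exp(−2 × 1.96/√377) = 0.817, stated as 0.82.
- OS boundaries by Lan-DeMets O'Brien-Fleming spending at 280, 342 and 428 deaths: p = 0.0112, 0.0210 and 0.0422, stated as 0.011, 0.021 and 0.042.

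No stated figure is in dispute, and none depends on the missing wording.

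**The texts side by side.**

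| Place | Names the DFS version that is controlled and opens OS? |
|---|---|
| Protocol synopsis (version 10) | Yes, US registrational |
| Protocol 6.1.1 and 6.4.1 | Yes, US registrational |
| SAP 2.2.1, 4.4.1, 4.4.2.1 | Silent |
| SAP Appendix 1 (version 8 synopsis) | Yes, US registrational |

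No row names the other version, and none says that either may serve. The precedence clause covers analyses that the SAP describes. An unqualified reference to the DFS results describes no different rule, so it displaces nothing. The version 8 label on Appendix 1 does not matter here, because version 10 keeps the same rule.

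**How often the two tests would disagree.** This needs q, the share of DFS events recoded as censored under the missed-visit rule. The documents give no value, so 2%, 5% and 10% are assumptions. A simulation of 20,000 trials per q used the plan's accrual, medians, loss to follow-up and visit schedule. It assumed hazard ratio 0.75, recoding at random and equally in both arms, an unstratified log-rank test, and 377 events counted without the missed-visit rule. The mean cutoff was Month 49.3, against Month 50 in the plan.

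| | q = 2% | q = 5% | q = 10% |
|---|---|---|---|
| Only the base version significant | 1.49% | 2.79% | 4.29% |
| Only the US version significant | 1.06% | 1.40% | 1.95% |
| Split (sum) | 2.55% | 4.19% | 6.24% |

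The split is a property of running two correlated tests. It would be the same if SAP 2.2.1 carried the protocol's parenthesis.

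**The permissive reading.** If either version could be claimed, the false-positive rate would be 1 − P(|Z₁| ≤ 1.96 and |Z₂| ≤ 1.96). For assumed correlations of 0.99, 0.975, 0.95 and 0.90 this is 0.057, 0.060, 0.065 and 0.070. Simulation under the null, with 8,000 trials per q, gives about 0.058, 0.057 and 0.061 for q = 2%, 5% and 10% (Monte Carlo standard error about 0.003). For those values of q the excess over 0.05 is roughly one percentage point, on a reading that no text supports.

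**The event trigger.** Neither document says which version counts toward the 377 events. If it is the base version, the controlled test has 377 × (1 − q) events, about 369, 358 and 339. The fair comparison is with base-version power from the same simulation:

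- q = 2%: 79.2 − 78.8 = 0.4 points
- q = 5%: 79.6 − 78.2 = 1.4 points
- q = 10%: 79.0 − 76.6 = 2.4 points

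The events-only formula at hazard ratio 0.75 gives larger losses: 79.8 − 79.0 = 0.8, 79.8 − 77.7 = 2.1 and 79.8 − 75.5 = 4.3 points. If the US version is counted, there is no loss.

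**The case for a change.** The best argument for a change is that the SAP paragraph was rewritten, not merely copied. SAP 4.4.1 requires the missed visits to be consecutive and adds a fallback to the randomization date. Protocol 6.4.1 has neither in its missed-visit rule. The type I error sentence that follows this rule in the protocol is absent from the SAP text. A reader cannot tell a slip from a decision, and the SAP claims precedence. Confirmatory status should be readable in the section headed type I error control, and repeating it there would cost one parenthesis and one sentence.

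Some of this stands. The omission is real, intent cannot be proved from the page, and repeating the rule would be tidier. But a deliberate change would need a replacement rule, and the SAP contains none. Its own Appendix 1 still states the protocol's rule. The concern about timing also loses force, because the answer to a split result is already written down in the protocol and does not wait for the data.

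The trigger question is separate. Protocol 6.1.2 and SAP 2.2.2 agree with each other, the target is approximate, and it is joined to a minimum of 12 months after the last enrolment. It is not an exact information target.

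**Conclusion.** No change to the plan is needed. SAP 2.2.1 and 4.4.1 leave out a detail that the protocol fixes and SAP Appendix 1 repeats, and nothing contradicts it. An analyst following the documents would test OS only if the US registrational DFS result is significant at two-sided 0.05. Repeating the rule in the SAP body would be an editorial convenience. It would not alter any test, alpha, event count, boundary or decision.

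The split rates of 2.6% to 6.2% and the power differences of 0.4 to 2.4 points (0.8 to 4.3 by formula) rest on assumed recoding shares. They describe having two DFS definitions, or an event-counting choice that the documents leave unstated. They do not measure an effect of the omitted wording. The conclusion depends on reading the SAP together with its appendix and the current protocol. It would change only if some text gave the role to the other DFS version, and none does.

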2.2.2 Primary Endpoint: Disease-Free Survival

The analysis of the primary endpoint of DFS will take place when approximately 377 DFS events have occurred in the intent-to-treat (ITT) population (defined in Section 4.1.1) and at least 12 months after the last patient is enrolled have elapsed.

The estimated number of events required for the analysis is based on the following assumptions:

- Two-sided, log-rank test at the 0.05 significance level (two-sided)
- 80% power
- 1:1 randomization ratio
- Median DFS for the control (observation) arm of 20 months and estimated median DFS in the atezolizumab arm of 26.7 months (corresponding to a HR of 0.75)
- No interim analysis for DFS

Accrual of the planned 800 patients is projected to occur over 32 months, assuming a ramp-up period of 13 months to a projected accrual rate of 35 patients per month. On the basis of these assumptions, and the projected probability of loss to follow-up for DFS of approximately 32% over 24 months after enrollment, the required number of DFS events is projected to occur at Month 50 from the time the first patient is randomized.

Also on the basis of these assumptions, it is projected that an observed HR of 0.82 or lower will result in a statistically significant difference between treatment arms (i.e., an HR of 0.82 will be the minimally detectable difference at the analysis; this corresponds to an improvement of 4.5 months in median DFS, from 20 months in the control [observation] arm to 24.5 months in the atezolizumab arm).

2.2.3 Secondary Endpoint: Overall Survival

The final analysis of the secondary endpoint of OS will take place when approximately 428 deaths have occurred in the ITT population on the basis of the following assumptions:

- Two-sided, log-rank test at the 0.05 significance level (two-sided)
- 80% power
- 1:1 randomization ratio
- Median OS for the control (observation) arm of 34 months and estimated median OS in the atezolizumab arm of 44.7 months (corresponding to HR of 0.76)
- Two interim analyses for OS (see Section 2.3.2 for details)

On the basis of these assumptions, the projected probability of loss to follow-up for OS of approximately 24% over 24 months after enrollment, and projected accrual, the required number of OS events for the final analysis of OS is projected to occur 95 months from the time the first patient is randomized. It is projected that an observed HR of 0.82 or lower will result in a statistically significant difference between treatment arms (i.e., an HR of 0.82 will be the minimally detectable difference at the analysis; this corresponds to an improvement of 7.4 months in median OS, from 34 months in the control [observation] arm to 41.4 months in the atezolizumab arm).

2.3 ANALYSIS TIMING

2.3.1 Primary Analysis Timing for DFS

No interim analyses are planned for the primary endpoint of DFS in this study. The analysis of the primary endpoint DFS will take place when approximately 377 DFS events have occurred in the ITT population and at least 12 months after the last patient is enrolled have elapsed. Based on the assumptions described in Section 2.2.2, the required number of DFS events is projected to occur at Month 50 from the time the first patient is randomized.

2.3.2 Interim and Final Analysis Timing for OS

There are no interim analyses planned for DFS, and a total of three analyses of OS will be performed by the Sponsor (two interim analyses and one final analysis; see Table 1 below for details about each analysis).

The first interim analysis of OS will be performed at the time of the DFS analysis. On the basis of the projected median OS for each treatment arm and the projected time of the final analysis of DFS, it is projected that approximately 280 deaths (35% of 800 patients)

will have occurred at the first interim analysis of OS, which corresponds to approximately 65% of the 428 deaths required for the final analysis of OS. It is projected that an observed HR of 0.74 or lower will result in a statistically significant difference between treatment arms at this analysis.

The second interim analysis of OS will be performed when approximately 342 deaths (43% of 800 patients) have occurred, which corresponds to 80% of the 428 deaths required for the final analysis of OS. The required number of OS events for the second interim analysis of OS is projected to occur at Study Month 63 from the time the first patient is randomized. It is projected that an observed HR of 0.78 or lower will result in a statistically significant difference between treatment arms at this analysis.

The final analysis of OS will take place when approximately 428 OS events have occurred in the ITT population. Based on the assumptions described in Section 2.2.3, the required number of OS events is projected to occur at Month 95 from the time the first patient is randomized. It is projected that an observed HR of 0.82 or lower will result in a statistically significant difference between treatment arms at this analysis.

The boundary for statistical significance at each interim analysis and the final analysis will be determined based on the Lan-DeMets implementation of the O'Brien–Fleming use function (Lan and DeMets 1983). For example, with $\alpha = 0.05$ (two-sided) and using the two-sided log-rank test, if 280 deaths have occurred at the time of the first OS interim analysis, statistical significance will be declared if $p \leq 0.011$; if 342 deaths have occurred at the time of the second OS interim analysis, statistical significance will be declared if $p \leq 0.021$; and if 428 deaths have occurred at the time of the final OS analysis, statistical significance will be declared if $p \leq 0.042$. The projected p-value boundary for statistical significance above is based on the number of projected events; actual boundary p-values will be calculated at the time of analysis based on the actual number of events observed in the ITT population.

Table 1 Overall Survival Interim and Final Analysis Characteristics

	ITT population n = 800
Target HR	0.76
median (observation arm)	34 months
median (atezolizumab arm)	44.7 months
Power	80%
Alpha level (two-sided)	0.05
Projected enrollment complete	Study Month 32
First interim OS (to be performed at time of final DFS analysis)	—
Projected cutoff date ^a	Study Month 50
Projected number of events (% of final events)	280 (65%)

	ITT population n = 800
Projected MDD ^b	0.74
Projected boundary (p-value) ^c	p ≤ 0.011
Second interim OS	—
Number of events (% of final events)	342 (80%)
Projected cutoff date ^a	Study Month 63
Projected MDD ^b	0.78
Projected boundary (p-value) ^c	p ≤ 0.021
Final OS	—
Number of events (% of final events)	428 (100%)
Projected cutoff date ^a	Study Month 95
Projected MDD ^b	0.82
Projected boundary (p-value) ^c	p ≤ 0.042

DFS = disease-free survival; HR = hazard ratio; MDD = minimally detectable difference; OS = overall survival

Note: The projected probability of loss to follow-up for OS of approximately 24% over 24 months after enrollment

^a Study month at which required number of events are projected to occur, where Study Month 1 is the month the first patient is enrolled. Analysis results will be available after data cleaning

^b The largest observed HR that is projected to be statistically significant

^c The projected boundary for statistical significance for the number of events shown (actual boundary to be calculated at time of analysis based on actual number of events).

